1.2 Wearables and physical activity

Until the introduction of wearables, physical activity was difficult to measure objectively or at scale. Traditionally, PA was studied using subjective measures such as surveys or diaries, or extremely expensive or intrusive objective measures such as doubly labelled water (DLW) or indirect calorimetry (16),(17),(18). The former methods can be applied in large population cohorts but are known to be subject to bias (17),(19). The latter provide highly accurate information about energy expenditure but provide no information about the underlying energy distribution (intensity) of that energy expenditure (20).

The advent of wearable technology has revolutionised the study of physical activity at a population level. A variety of estimation techniques, ranging from uniaxial accelerometers to combined heart rate and movement sensors, have been used to study a diverse range of population cohorts (11),(21),(22),(23),(24). As a result, physical activity researchers have been able to look beyond simple metrics like time in MVPA to more biologically based phenomena. This has seen a shift from descriptive to aetiological studies that link an individual's average daily PAEE, or their underlying intensity composition, with disease states (25),(26),(27).

Of the methods currently available, triaxial accelerometers such as the GENEActive Device (Activinsights, UK; Figure 2) are emerging as a favoured device amongst physical activity researchers. Compared to other methods, the devices are well tolerated, can be placed on a variety of sites throughout the body, are worn 24 hours a day, are relatively inexpensive,

reusable, and are validated against the gold standard DLW in a British population (22),(28). Furthermore, as wrist-worn devices, they are suitable for use in orthopaedic patients with previous lower limb arthroplasty. Alternative devices include the thigh-worn Axivity AX3 3-Axis Logging Accelerometer (Axivity, UK; Figure 3). These are versatile, lightweight devices that have been validated against other monitors (29).

Figure 2. GENEActive triaxial accelerometer (Activinsights, UK)

[figure not shown]

Figure 3. Axivity AX3 3-Axis Logging Accelerometer (Axivity, UK)

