1.3 Physical activity and common treatments for severe arthritis

Joint replacement is widely heralded as a safe and effective option for patients with end-stage arthritis, as patients report improved function and less pain. However, the statistic used to describe the success of the procedure is that of 'implant survival', which specifically ignores the more important metric of 'patient survival' (30). The two graphs below, from the National Joint Registry of England and Wales, illustrate this paradox: Figure 3A shows the unattractive higher mortality risks associated with total knee replacement, while Figure 3B shows the attractive low risk of revision surgery for the procedure.

[figure not shown]

Figure 3. Implant and patient survival post-knee replacement (30).

In earlier work from our group, we have published the substantial differences in gait characteristics between patients with different types of surgical procedures (31),(32),(33). However, any extrapolation from these small laboratory-based studies would be theoretical. Our best explanation for the profound difference in mortality, in the longer term, between more and less radical procedures is that patients who are allowed to retain more of their own bodies feel more normal and thus enjoy more activity. Alternatively, patients with large stiff metal implants substituting large parts of their femur and tibia are not expected to feel 'normal' ever again. To test this explanation, we propose to study physical activity of two groups of patients who participated in a previous study (34). In the current study, we want to explore whether physical activity levels varies between these two groups 15 years after their index surgery.

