2. OBJECTIVES

2.1 Primary Objective:

To compare the volume and intensity of physical activity 15 years after surgery in patients after hip resurfacing and total hip replacement.

2.2 Secondary Objective(s):

To explore the association between the participants' physical activity and functional outcome scores.

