3. STUDY DESIGN

This is a cross-sectional observational (follow-up) study in which we will ask participants to complete four paper questionnaires, wear a tri-axial accelerometer on their non-dominant wrist continuously for ten days and nights, and simultaneously wear a tri-axial accelerometers taped to the surgical thigh for a period of 48 hours.

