8. METHODS

8.1 Study parameters/endpoints

8.1.1 Main study parameter/endpoint

In order to gain insight into the volume and intensity of physical activity, both the wrist-worn GENEActiv triaxial accelerometer and the thigh-worn Axivity AX3 Logging tri-axial accelerometers will measure physical activity energy expenditure (PAEE) (7) and the intensity distribution of PAEE (7),(8). The wrist worn GENEActiv triaxial accelerometer will additionally measure the participants' step count (28),(35).

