10. STATISTICAL ANALYSIS

10.1 Primary study parameter(s)

Following the devices' return to the researcher, the recorded data will be downloaded and stored securely in a dedicated study folder on Rijnstate's digital network. The raw triaxial wrist and thigh acceleration data will be auto-calibrated to local gravitational acceleration (in g) and then converted to a Vector Magnitude (VM). VM, or Euclidean Norm, can be interpreted as the magnitude of acceleration the device was subjected to at each measurement, including gravitational acceleration. Non-wear detection procedures will be applied, and any such non-wear periods will be excluded from these analyses. The acceleration signal will be summarised to a common time resolution of one observation per minute and subjected to prediction models

to calculate physical activity energy expenditure, time in moderate-to-vigorous physical activity, and step count.

Raw accelerometry data will be processed using the R-project for Statistical Computing and open-source packages (R Foundation for Statistical Computing, Vienna, Austria). Statistical analysis will be conducted using STATA/SE version 17 (StataCorp, College Station, TX, USA). For descriptive statistics, we will report medians (interquartile ranges) or means (standard deviations) for continuous variables and proportions for categorical variables. To examine face validity and the performance of each multi-level linear regression model, we will conduct ANOVA repeat measures analysis to calculate Pearson's coefficient and Root Mean Squared Error metrics. Differential bias will be assessed by age, sex, and BMI categories.

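### Should the differential-bias check in section 10.1 also be split by implant group, with a named reference for Pearson's coefficient and RMSE?

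*Combined protocol and SAP*

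**What the plan says.** The primary objective (section 2.1) is "To compare the volume and intensity of physical activity 15 years after surgery in patients after hip resurfacing and total hip replacement". Section 8.1.1 says that "both the wrist-worn GENEActiv triaxial accelerometer and the thigh-worn Axivity AX3 Logging tri-axial accelerometers will measure physical activity energy expenditure"; step count comes from the wrist device only. The wrist device is worn for ten days. Under section 3, participants also "simultaneously wear a tri-axial accelerometers taped to the surgical thigh for a period of 48 hours".

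Section 10.1 obtains PAEE, time in moderate-to-vigorous activity and step count from prediction models applied to minute-level acceleration. It then plans Pearson's coefficient and RMSE, with this purpose: "To examine face validity and the performance of each multi-level linear regression model". The bias check follows: "Differential bias will be assessed by age, sex, and BMI categories". Implant group is not named anywhere in section 10, and no reference is given for the two metrics.

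Two background statements bear on the point. Section 1.2 says of the wrist monitors that "as wrist-worn devices, they are suitable for use in orthopaedic patients with previous lower limb arthroplasty". Section 1.3 reports "substantial differences in gait characteristics between patients with different types of surgical procedures" from the group's own work, and adds that "any extrapolation from these small laboratory-based studies would be theoretical".

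**The concern.** The endpoints are model predictions, and the plan itself allows that their error may vary between kinds of patient. A bias linked to age, sex or BMI reaches the RHA-THA contrast only if the groups are unbalanced on that factor. A bias linked to the implant would go straight into it. The thigh monitor sits on the operated leg, gait is said to differ by procedure, and section 10.1 does not say which device's PAEE is primary. If thigh-based PAEE erred differently in the two groups, the comparison could shift without readers being able to see it.

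The missing reference adds to this. Pearson's coefficient and RMSE each need two series. Doubly labelled water appears only as earlier validation in section 1.2, and section 8.3 collects neither that nor calorimetry.

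**Working it through.** **1. What the text supports.** The plan gives no SD, effect size, power or sample-size calculation, so there is no stated figure to reproduce. Three readings of the Pearson/RMSE sentence remain open:

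- observed against fitted values, since the sentence concerns regression models and the observed outcome would then be the reference;
- accelerometer against the IPAQ-SF or SQUASH questionnaires (section 8.1.2);
- wrist against thigh over the shared 48 hours, which is 48/240 = 0.20 of the wrist record.

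The sentence is ambiguous, but it has workable readings.

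**2. Evidence for an implant-dependent error.** Three references support the gait sentence in section 1.3. By title, 31 and 32 are knee studies and only 33 compares hip resurfacing with total hip replacement. The title of reference 34, the parent trial, also reports a gait difference by implant. A gait difference is not a PAEE error, and no document gives such an error or its size.

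**3. What a wrist-thigh check by implant could resolve.** Inputs from the documents: 34 RHA and 26 THA (section 4). Section 8.2 gives 82 randomised beside the same two group sizes, so 60 is itself an assumption. Further assumptions: equal wrist and thigh SDs; wrist-thigh correlation r from 0.5 to 0.9; PAEE SD 30% of the mean; and, as a lower case, half of each group taking part (17 and 13).

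The quantity is the RHA minus THA difference in mean thigh-minus-wrist PAEE. Its 95% CI half-width in SD units is

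t(0.975, n − 2) × √(2(1 − r)) × √(1/n₁ + 1/n₂).

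- 34/26: t = 2.002 and √(1/34 + 1/26) = 0.2605, product 0.5215.
- 17/13: t = 2.048 and √(1/17 + 1/13) = 0.3684, product 0.7547.

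Multiplying by √(2(1 − r)) gives SD units, and then by 0.30 gives a percentage of the mean:

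| r | √(2(1 − r)) | 34/26: SD | 34/26: % of mean | 17/13: SD | 17/13: % of mean |
|---|---|---|---|---|---|
| 0.9 | 0.447 | 0.233 | 7.0 | 0.338 | 10.1 |
| 0.8 | 0.632 | 0.330 | 9.9 | 0.477 | 14.3 |
| 0.7 | 0.775 | 0.404 | 12.1 | 0.585 | 17.5 |
| 0.5 | 1.000 | 0.521 | 15.6 | 0.755 | 22.6 |

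At r = 0.5 the half-width equals that of the RHA-THA contrast in a single device's PAEE (0.52 or 0.75 SD).

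**4. Power.** An error that just equals the half-width is detected only about half the time. The calculation uses the noncentral t distribution (two-sided 5%, SD 30% of the mean), with noncentrality (error/0.30) / [√(2(1 − r)) × √(1/n₁ + 1/n₂)]. For a 10% error at r = 0.8 with all 60 this is 0.333/(0.632 × 0.2605) = 2.02.

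| r | 34/26: 5% error | 34/26: 10% error | 17/13: 5% error | 17/13: 10% error |
|---|---|---|---|---|
| 0.9 | 29% | 80% | 16% | 50% |
| 0.8 | 17% | 51% | 11% | 28% |
| 0.5 | 10% | 24% | 7% | 14% |

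**5. Sensitivity to the SD.** For r from 0.9 to 0.5 the half-width is 4.7% to 10.4% of the mean (60 patients) and 6.8% to 15.1% (30 patients) if the SD is 20% of the mean. With an SD of 40% it is 9.3% to 20.9% and 13.5% to 30.2%. Only the favourable corner (SD 20%, r near 0.9, full participation) resolves a 10% error comfortably.

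**6. What the estimate would mean.** With no criterion measure, a difference between implants cannot show which device is wrong and misses error common to both sites. It could also arise from a true difference in type of activity, or from an error proportional to activity when true activity differs. It does not isolate bias.

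**The case for a change.** The best argument for a change is that it costs a few sentences and a few lines of code. Both monitors are already worn together, and settling the pair and the subgroups before data are seen removes a choice that could otherwise be made afterwards. For any r above 0.5, with equal SDs, the device-by-implant difference is estimated more precisely than the group contrast in either device alone. The age, sex and BMI checks already planned face the same limit on numbers, so low precision is not by itself a reason to omit implant group.

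The points on cost and relative precision stand, and naming the compared pair would make the plan clearer. They do not show that following the plan as written gives a worse answer. Requiring wrist against thigh as the reference would also impose a pair that the plan does not state. The result would still be agreement between devices, which cannot correct the RHA-THA estimate or say which version of it to believe.

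**Conclusion.** No change follows. The omission of implant group and the unnamed comparator are accurate observations about section 10.1. The comparator is a detail that analysts have to fix in order to compute the metrics at all, and they would state it when reporting. A split by implant is an optional supplementary table: data already being collected allow it, but no primary result or conclusion depends on it.

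With all 60 patients and an SD of 30% of the mean, such a table would have a half-width of 7.0% to 15.6% of the mean and at most 29% power for a 5% error. Power for a 10% error reaches 80% only at r of about 0.9. If it is produced, it should be labelled as device agreement, and an interval that includes zero should not be read as absence of bias.

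This rests on the assumed correlations, SD and participation, none of which the documents give, and on the absence of any documented implant-dependent PAEE error. It is also unknown whether a thigh error would reach the primary contrast, because section 10.1 does not name the primary device.

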4. STUDY POPULATION

We will only approach patients that have participated in a previous randomised controlled trial (34) that was conducted in Rijnstate hospital between 2007-2008. These include 34 patients after hip resurfacing and 26 patients after total hip replacement.

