8.2 Randomisation, blinding and treatment allocation

In this observational (follow-up) study participants will not be randomised, blinded or treated. The potential participants for this current study have previously participated in a randomised controlled trial. In this RCT (34), a total of 82 patients were randomly assigned to receive resurfacing hip arthroplasty (RHA, $n = 34$) with a 6-mm thick cobalt-chromium cup or conventional total hip arthroplasty (THA, $n = 26$) with a more conical threaded titanium cup. All participants of this previous RCT will be contacted to ask if they are willing to participate in this follow-up study.

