12. ADMINISTRATIVE ASPECTS, MONITORING AND PUBLICATION

12.1 Handling and storage of data and documents

All data handling and storage will comply with the EU General Data Protection Regulation and the Dutch Act on Implementation of the General Data Protection Regulation (Dutch: Uitvoeringswet AVG). All data collected during this study will be managed according to the FAIR principles in order to enhance and improve Findability, Accessibility, Interoperability and Reuse of research data.

All patient data will be handled confidentially. Each subject will be given an identification code and only the investigators involved in this study will have access to the subject identification code list which can be used to link the data to the patient. The code list and all raw patient data will be stored in a designated research folder on Rijnstate's local computer mainframe.

The Rijnstate coordinating investigator/project leader will collect the patient source data from the electronic patient records. These data comprise the participant's hospital identification number, age, gender, Body Mass Index (BMI), the presence and severity of any cardiovascular, pulmonary or neuromuscular diagnoses, and the use of medications for these diagnoses. After full data collection, data will be transferred to STATA/SE version 17 (StataCorp, College Station, TX, USA). In this spreadsheet the participant data will be non-identifiable/anonymous. All accelerometer and patient-related (questionnaire) data will be coded and securely shared with the UK investigators via Surf Filesender (<https://www.surf.nl/en/services/surffilesender>). All data collected during this study will be kept under secure conditions at Rijnstate Hospital for 15 years after the research has ended and then it will be destroyed. Any information collected will be treated as confidential and used only in this study unless otherwise specified. All source data relating to consented study participants will be stored and processed in line with Rijnstate Hospital requirements. All source data held in paper form (Informed Consents) will be scanned and securely stored as soon as possible after the participant has signed it. Paper copies will be stored in the secured research lockable cabinet at the department of Orthopaedics of Rijnstate.

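### Differential bias is to be checked by unspecified BMI (and apparently age) categories in about 60 people; keeping age and BMI continuous would make a moderate bias harder to miss

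*Combined protocol and SAP*

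**What the plan says.** The plan's only statement on this check closes section 10.1: "Differential bias will be assessed by age, sex, and BMI categories". It follows the sentence on model performance, "To examine face validity and the performance of each multi-level linear regression model, we will conduct ANOVA repeat measures analysis", which goes on to name Pearson's coefficient and root mean squared error. The section states no number of categories, cut-points, test, reference measure, or size of bias that would matter.

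Section 12.1 lists age and BMI among the items taken from the electronic patient records and mentions no grouping. It is reasonable to infer that numeric values will be available, though the plan does not say so. The regression in section 10.2 concerns the questionnaire outcomes, so no continuous analysis of this check appears elsewhere.

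On numbers, section 4 says "These include 34 patients after hip resurfacing and 26 patients after total hip replacement". Section 8.2 says "a total of 82 patients were randomly assigned to receive resurfacing hip arthroplasty", followed by the same arm sizes of 34 and 26, and then "All participants of this previous RCT will be contacted to ask if they are willing to participate in this follow-up study".

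**The concern.** The main endpoint is derived from prediction models applied to accelerometer signals. This check is the one step in section 10.1 that asks whether those estimates behave alike in older and younger, heavier and lighter, male and female participants. If age and BMI are cut into classes in a sample this small, each class holds few people and the comparison rests on noisy class means. A bias that moves steadily with age or BMI is then easier to miss. A finding of no differential bias could be taken as reassurance that the check was too insensitive to give. The numeric values should already be in the data set, so the loss is avoidable.

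**Working it through.** **Inputs from the documents.** Patients available: 34 + 26 = 60 (section 4). Section 8.2 gives 82 randomised, which is 22 more than its own arm sizes add up to. The plan has no power, alpha or precision figure for this check, so there is no stated result to reproduce.

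**Assumptions.** Two-sided 5% test; covariate normally distributed; true correlation between error and covariate of 0.30 to 0.50, with 0.35 as the main case; sample sizes from 40 to 82. None of these is in the plan.

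**Step 1: information kept after grouping.** For a standard normal covariate and a linear bias, the share kept is the between-class share of the covariate's variance, Σ pⱼmⱼ². Here pⱼ is the class proportion and mⱼ the class mean, mⱼ = [φ(a) − φ(b)]/pⱼ for a class running from a to b.

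- Median split: m = ±0.399/0.5 = ±0.798, so the share kept is 0.798² = 2/π = 0.637. Loss 36%; 60 people carry the information of 60 × 0.637 ≈ 38.
- Tertiles: share kept 0.793. Loss 21%.
- Quartiles: share kept 0.861. Loss 14%.
- BMI cut at 25 and 30, with an assumed mean of 26 to 28 and SD of 4 to 4.5: share kept 0.79 to 0.81. Loss 19–21%.
- Unequal two-group split, 20/80: share kept 0.490. Loss 51%.
- Uniform rather than normal covariate: losses of 25%, 11% and 6% for two, three and four equal groups.

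**Step 2: power by simulation, linear bias.** The continuous analysis tests the slope. The median split is a t test, and the unordered tertile test is a 2-df ANOVA.

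| n | Correlation | Continuous | Median split | Tertiles, 2 df | Tertile trend |
|---|---|---|---|---|---|
| 60 | 0.30 | 66% | 46% | 44% | 55% |
| 60 | 0.35 | 79% | 59% | 57% | 69% |
| 60 | 0.40 | 90% | 71% | 71% | 81% |
| 60 | 0.50 | 99% | 91% | 92% | 96% |
| 40 | 0.40 | 74% | 53% | 51% | 63% |
| 82 | 0.35 | 91% | 73% | 73% | 83% |

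Unordered quartiles at n = 60 and correlation 0.35 give 55–56%. Repeat simulations of the 0.35 row agree within one or two percentage points. In that row a real bias is missed about 4 times in 10 with a two-group or unordered test, against 2 in 10 with the continuous value.

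**Step 3: a bias that is not a straight line.** Still at n = 60, with a U-shaped bias explaining 16% of the error variance (assumed), a straight-line slope has about 12% power. Unordered tertiles and quartiles have 23–31%, and a joint 2-df test of linear and quadratic terms has about 77%. When the bias is purely linear with correlation 0.35, the same joint test has about 69%, against 79% for the slope alone and 56–58% for unordered tertiles or quartiles.

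**Step 4: what sample size alone limits.** The smallest correlation detectable with 80% power on the continuous scale is tanh[(1.960 + 0.842)/√(n − 3)]. At n = 60 this is tanh(2.802/7.550) = 0.35; at n = 40 it is 0.43; at n = 82 it is 0.31.

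**The case against.** Several points on the other side carry weight.

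The plan states no test for this check. It may intend no more than a descriptive table of bias by subgroup, in which case power does not strictly apply. That is a fair reading, but wide, overlapping class means hide a trend from the eye much as they hide it from a test.

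Part of the loss shown for tertiles and quartiles comes from the unordered multi-df test and not from grouping itself. Quartiles keep more information than a median split, yet show slightly lower power. A tertile trend test recovers about half of the tertile loss. This stands, and it is why the trend figure is given alongside; even that test falls about 10 points short of the continuous analysis at correlation 0.35.

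A single straight line is not always better than categories. Step 3 shows that it can be worse for a U-shaped bias. This also stands, and it is the reason for a quadratic term.

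The gap narrows when the bias is strong: at correlation 0.50 it is 99% against 91% for a median split and 96% for a tertile trend.

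A reader might infer that a third of the information is lost as a matter of fact. The documents do not support that, because it holds only for a near-median two-group split of a roughly normal covariate, and the plan states no cut-points. A reader might also infer a firm ceiling of 60 participants. Section 8.2's figure of 82, and its intention to contact everyone in the earlier trial, leave that unsettled. Finally, the grammar allows the categories to apply to BMI alone, and sex loses nothing in any case.

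**Conclusion.** The point holds as a minor one. Grouping BMI, and apparently age, in about 60 people costs sensitivity that could be kept without new data. For a moderate linear bias (correlation 0.35, assumed) the cost is roughly 20 percentage points of power with a two-group or unordered test, and about 10 with a tertile trend. The loss persists at n = 82 (91% against 73%) and at n = 40 with correlation 0.40 (74% against 51–53%), so it does not depend on which headcount is right. The exact loss cannot be fixed until the categories are stated.

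Two limits apply. Small numbers are a separate cause of low sensitivity: even with continuous covariates, 60 people give 80% power only for correlations of about 0.35 or more. And a reader might infer that the main result is undermined. The documents do not support that, since this is a subsidiary check on the activity estimates, no decision in the plan is tied to it, and the resurfacing versus total hip replacement comparison does not use these categories.

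**What to change.** In section 10.1, first name the quantity whose bias is assessed and the reference it is measured against; until that is done, neither a table nor a model can be computed. Then model that quantity on continuous age and continuous BMI, each with a quadratic term if numbers allow, and sex as a factor. Report the estimates with 95% confidence intervals, for example per 10 years and per 5 kg/m² where a linear term suffices, and avoid resting the conclusion on a non-significant test. Keep a category table for description, with its cut-points stated in advance. Reconcile the 60 in section 4 with the 82 in section 8.2.

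The cost is a few sentences and no new data. The trade-off is that a quadratic term gives up some power when the bias is purely linear (about 69% against 79% in the main case) in exchange for much better detection of a curved one (about 77% against 12%).
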